### **5.12.3. Percentage of Patients Achieving a Target HbA1c <7.0%**

For percentages of patients achieving target HbA1c of <7.0 at 24 weeks, longitudinal logistic regression with repeated measurements (generalized linear mixed models, Liu and Zhan 2011) will be used. The model will include independent variables for treatment, country, SGLT2 inhibitor dose (“low” versus “high”), metformin use (“yes” versus “no”), visit, baseline HbA1c - by-visit interaction, and the treatment-by-visit interaction as fixed effects, and baseline HbA1c as a covariate. These analyses will be performed with post-rescue data excluded (considered missing), and separately with all post-rescue data included. In addition, an analysis of percentage of patients on HbA1c targets will be performed where patients who have been rescued or have no post-baseline data will be considered (imputed) as not having achieved the target.

## **5.13. Other Secondary Efficacy Analysis**

### **5.13.1. Analysis of Fasting Glucagon**

Change of fasting glucagon will be summarized using ITT population. Change from baseline of fasting glucagon will be analyzed using ANCOVA model with LOCF includes treatment, country, SGLT2 inhibitor dose (“low” versus “high”), metformin use (“yes” versus “no”), baseline HbA1c strata ( $\leq 8.0\%$  and  $> 8.0\%$ ) as fixed effects, and baseline (fasting glucagon as a covariate (with and without post rescue data).

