**Table GBGE.4.1. Objectives and Endpoints**

Objectives	Endpoints

Primary To demonstrate that once-weekly dulaglutide (1.5 mg and/or 0.75 mg) is superior to placebo as measured by HbA1c at 24 weeks (change from baseline) in patients with inadequately controlled T2D on concomitant SGLT2 inhibitor therapy.
	
 
• The change in HbA1c from baseline to 24 weeks
 

Secondary Key secondary efficacy objectives (controlled for type 1 error) are to compare dulaglutide 1.5 mg and 0.75 mg to placebo at 24 weeks
 
Other secondary efficacy objectives are to compare dulaglutide 1.5 mg and 0.75 mg to placebo at 24 weeks
 
Secondary safety objectives are to compare dulaglutide 1.5 mg and 0.75 mg to placebo at 24 weeks
	
 
• Proportion of patients with HbA1c target values of <7.0% at 24 weeks
 
• The change in FBG (central laboratory) from baseline to 24 weeks
 
• The change in body weight from baseline to 24 weeks
 
 
 
• Proportion of patients with HbA1c target values of ≤6.5% at 24 weeks
 
• The change in 6-point SMPG profile from baseline to 24 weeks
 
• The change in fasting glucagon from baseline to 24 weeks
 
 
Incidence of:
 
 
• Treatment-emergent adverse events (TEAEs)
 
• Early discontinuations due to AEs
 
• Adjudicated cardiovascular and pancreatic AEs
 
• Thyroid neoplasms AEs
 
• AEs related to kidney failure, eGFR
 
• Systemic hypersensitivity AEs
 
• Local injection site reactions
 
• The change in systolic and diastolic blood pressure, heart rate, and lipids from baseline to 24 weeks
 
• Incidence and rate of hypoglycemic episodes
 
• Ketoacidosis, and initiation of rescue therapy for severe persistent hyperglycemia
 

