The baseline will be Visit 5, except for HbA1c. Patients who do not need stabilization will have blood drawn for baseline HbA1c at Visit 2, and those who need stabilization at Visit 4. For all variables except HbA1c, if baseline data are missing, the last nonmissing measurement taken prior to Visit 5 will be used for the baseline measurement. For HbA1c, if baseline data are missing, the imputation will be conducted only if an additional value between Visit 2 and randomization (patients not needing stabilization) or Visit 4 and randomization (patients needing stabilization) is collected. The endpoint for the primary analysis is defined as the change from baseline in HbA1c at 24 weeks (Visit 11). Key secondary endpoints are percent to goal in HbA1c (<7.0%) at 24 weeks and change from baseline in FBG (central laboratory) and body weight at 24 weeks.

Two analysis models will be used for the primary and key secondary continuous efficacy measures. The primary analysis will be mixed-model repeated measure (MMRM) analysis using restricted maximum likelihood (REML). An unstructured covariance structure will be used to model the within-patient errors. If this model fails to converge, the following covariance structures will be tested in order:

- Toeplitz with heterogeneity
- autoregressive with heterogeneity, by visit
- compound symmetry with heterogeneous variances by visit,
- Toeplitz
- autoregressive
- compound symmetry without heterogeneous variances, by visit

The first covariance structure that converges will be used.

The secondary analysis for the primary and key secondary continuous endpoints will be analysis of covariance (ANCOVA). Missing endpoints will be imputed with the last (postbaseline) observation carried forward (LOCF). The percentage of patients achieving the target HbA1c of <7.0% at 24 weeks will be analyzed using a longitudinal logistic regression with repeated measurements.

A graphical testing approach will be used to strongly control for type 1 error to test for superiority of each of the dulaglutide doses versus placebo at 24 weeks for the following

measures: (1) change from baseline in HbA1c, (2) change from baseline in FBG (central laboratory), (3) percent achieving HbA1c <7.0%, and (4) change from baseline in body weight.

[figure not shown]

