### **5.12.2. Analysis of Fasting Blood Glucose**

Change from baseline in FBG will be summarized using the ITT population. This variable will be analyzed using the ANCOVA model with LOCF which includes treatment, country, SGLT2 inhibitor dose (“low” versus “high”), metformin use (“yes” versus “no”), baseline HbA1c strata ( $\leq 8.0\%$  and  $> 8.0\%$ ) as fixed effects, and baseline (FBG) as covariate.

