### **5.13.3. Analysis of 6-point SMPG profile**

The 6-point self-monitored plasma glucose (SMPG) profiles consist of pre-meal and 2-hour postprandial SMPG measurements for the morning, midday, and evening meals.

The following variables for 6-point SMPG profile will be analyzed using MMRM:

1. Pre morning meal plasma glucose (PG) (mg/dL)
2. 2-hour postprandial measurement for morning meal PG (mg/dL)
3. Pre midday meal PG (mg/dL)
4. 2-hour postprandial measurement for midday meal PG (mg/dL)

5. Pre evening meal PG (mg/dL)
6. 2-hour postprandial measurement for evening meals PG (mg/dL)
7. Mean of all pre-meals PG (mg/dL)
8. Mean of all postprandial PG (mg/dL)
9. Mean of all meals 2-hr excursion (mg/dL)
10. Mean of all 6-point PG (mg/dL)

For mean of all pre-meals PG (Report 7), the pre-meal daily mean is calculated as the average PG values collected for before morning, midday and evening meals on a particular day. The change from baseline is calculated as the mean of all pre-meals PG at Week 12 and Week 24 minus the mean of all pre-meals PG at baseline.

For mean of all postprandial PG (Report 8), the post-meal daily mean is calculated as the average of 2-hour postprandial PG values of morning, midday and evening meals on a particular day. The change from baseline is calculated as the mean of all postprandial PG at Week 12 and Week 24 minus the mean of all postprandial PG at baseline.

For mean of all meals 2-hour excursion at each visit (Report 9), the daily mean for all meals is calculated as the average of glucose excursion for morning, midday and evening meals on a particular day. The change from baseline is calculated as the mean of all meals 2-hour excursion at Week 12 and Week 24 minus the mean of all meals 2-hour excursion at baseline.

For mean of all 6-point PG (Report 10), the daily mean is calculated as the average of 6 PG values collected on a particular day. The change from baseline is calculated as the mean of all 6-point PG at Week 12 and Week 24 minus the mean of all 6-point PG at baseline.

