Change from baseline of 6-point SMPG values will be summarized using the ITT population, and analyzed using MMRM with treatment, country, SGLT2 inhibitor dose (“low” versus “high”), metformin use (“yes” versus “no”), visit, baseline HbA1c strata ( $\leq 8.0\%$  and  $> 8.0\%$ ) and treatment-by-visit interaction as fixed effects, baseline 6-point SMPG as a covariate and patient as a random effect. An unstructured covariance structure will be used to model the within-patient variability and implicitly adjusts for missing data. If this analysis fails to converge, then other covariance structures will be tested in the order mentioned in Section 5.2.

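### Fasting glucagon change to 24 weeks is analysed only by ANCOVA with LOCF, with no analysis that relaxes the carry-forward assumption (minor)

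*SAP*

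**What the plan says.** The objectives table (Table GBGE.4.1) lists the endpoint among the other secondary efficacy objectives as "The change in fasting glucagon from baseline to 24 weeks".

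Section 5.13.1 names one model: "Change from baseline of fasting glucagon will be analyzed using ANCOVA model with LOCF". Its terms are treatment, country, SGLT2 inhibitor dose, metformin use and baseline HbA1c stratum, with baseline glucagon as covariate. It is run "with and without post rescue data". The section names no repeated-measures model, no multiple imputation and no other way of handling a missing Week 24 value.

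Three other places give context:

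- Section 5.2 puts MMRM first and LOCF-ANCOVA second, but limits that order: "Two analysis models will be used for the primary and key secondary continuous efficacy measures". It describes LOCF as filling a missing endpoint with the last post-baseline value.
- Section 5.13.3 covers the only other continuous endpoint in the same tier: "The following variables for 6-point SMPG profile will be analyzed using MMRM", with changes defined at Weeks 12 and 24. It says that the unstructured covariance "will be used to model the within-patient variability and implicitly adjusts for missing data".
- Section 5.12.2, on fasting blood glucose, also names LOCF-ANCOVA alone: "This variable will be analyzed using the ANCOVA model with LOCF which includes treatment, country".

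**The concern.** The endpoint is a change at a fixed time, but LOCF fills missing Week 24 values with whatever was measured last. The estimate then mixes time points. If the drug effect on glucagon is still building when patients leave, the contrast is diluted. If it wanes later, the contrast is inflated. If dropout or rescue differs by arm, a time trend common to all arms can produce a difference without any drug effect.

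The two planned runs do not help, because both carry values forward. Their agreement would show insensitivity to post-rescue data and would say nothing about LOCF. In the run without post-rescue data, a rescued patient's pre-rescue value is carried as well, so more patients are affected.

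Single imputation also treats the carried value as measured, so the standard error does not reflect that it was imputed.

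At stake is the reported estimate and interval for a supportive endpoint.

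**Working it through.** **The plan's own figures.** The SAP states no figure for glucagon. Its only design calculation (section 5.1) is for HbA1c and supplies the dropout rate, so it is checked first.

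- Inputs: difference 0.55, SD 1.2, two-sided alpha 0.025, power 90%, dropout 15%, screen failure 40%.
- n per arm = 2 × (2.241 + 1.282)² × (1.2/0.55)² = 118.2, so 119, against 120 stated. Power at 120 per arm is 90.5% (90.1% by the noncentral t), against 90% stated.
- 120/0.85 = 141.2, so 142 per arm; 3 × 142 = 426; 426/0.60 = 710. All reproduce.

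**Patients affected.** 0.15 × 142 = 21.3 per arm; 0.15 × 426 = 63.9 in total. These are planned dropouts. The number with a carried glucagon value is smaller if some have no post-baseline sample, and larger in the run without post-rescue data, where rescued patients are added.

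**Bias in the treatment effect.** Let d be the share of values carried forward and f the fraction of the Week 24 effect already present in a carried value. Assume that d is equal in both arms and that dropouts would have shown the same Week 24 effect as the others. Then

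LOCF estimate / true Week 24 effect = (1 − d) + d × f.

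With d = 0.15:

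| f (assumed) | Ratio |
|---|---|
| 0 | 0.850 |
| 0.25 | 0.8875 |
| 0.5 | 0.925 |
| 0.75 | 0.9625 |
| 1 (plateau) | 1.000 |
| 1.5 (effect later wanes) | 1.075 |

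At d = 0.20, for instance if rescue censoring is added, the range for f from 0 to 1.5 is 0.80 to 1.10.

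**Bias with no drug effect.** Assume 20% missing in one arm, 10% in the other, and a common time trend of 0.3 SD that is half complete at dropout. Each carried value is then 0.15 SD short, and the false difference is (0.20 − 0.10) × 0.15 = 0.015 SD. With 142 per arm the standard error is √(2/142) = 0.119 SD, so the shift is 0.015/0.119 = 0.13 standard errors. A nominal 5% two-sided test would then reject at about 5.2%.

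**Precision.** Counting carried values as observed raises the nominal n from 120 to 142 per arm. With equal variance (assumed), the standard error falls by the factor √(120/142) = 0.919, about 8% below that for completers alone. Not all of this is spurious, because earlier samples carry some information about Week 24.

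**The case against.** The strongest objection is that the SAP gives no glucagon sampling visits, and a schedule properly belongs to the protocol. If glucagon is sampled only at baseline and Week 24, an MMRM adds essentially nothing to ANCOVA, and there is little for LOCF to carry beyond an early-termination or unscheduled sample. This stands as far as the remedy goes: the documents do not establish that glucagon is measured repeatedly, so MMRM cannot be prescribed outright. It does not rescue the plan. With several post-baseline samples, LOCF alone is the weaker choice. With one, LOCF either carries an off-schedule value to Week 24 or does nothing, and the analysis is then complete-case in effect.

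A reader might infer three stronger points that the document does not support:

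- *That section 5.13.1 contradicts section 5.2.* The MMRM-first order covers primary and key secondary measures only, and glucagon is neither.
- *That the SAP chose MMRM for SMPG because of missing data, and so admits LOCF is inadequate for glucagon.* Section 5.13.3 describes a property of the model and gives no reason for choosing it.
- *That glucagon is the odd one out.* Fasting blood glucose also has LOCF-ANCOVA alone in its own section. As a key secondary endpoint it falls under the section 5.2 rule, so that mismatch is a separate and more serious matter.

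It is also fair to say that the magnitudes rest on assumed inputs, that the false difference with no drug effect is negligible, and that section 5.2 leaves room for additional exploratory analyses. All of this stands and keeps the point minor. An unspecified later analysis is still a poor substitute for a prespecified one.

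**Conclusion.** The point holds as a minor weakness in the choice of analysis. For an endpoint fixed at 24 weeks, the SAP prespecifies only LOCF-ANCOVA, and both planned runs share that assumption. With 15% carried forward equally in both arms, the estimate could be 85% to 107.5% of the true effect as f runs from 0 to 1.5. The bias can go either way and is zero at a plateau. The standard error could be up to about 8% smaller than that for completers, only part of which is earned. These figures rest on an assumed time course, on planned HbA1c-study dropout standing in for missing glucagon values, and on every dropout having an earlier post-baseline sample.

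No confirmatory conclusion depends on the result: glucagon is not among hypotheses H1 to H8 of the graphical scheme and plays no part in the sample size.

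**What to change.** In section 5.13.1, state the scheduled glucagon visits or refer to the protocol's schedule, and then:

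- **More than one scheduled post-baseline sample:** make the main analysis an MMRM with the section 5.13.3 terms, including treatment-by-visit, with baseline glucagon as covariate and the Week 24 contrast reported. Use the section 5.2 order of covariance structures if it fails to converge.
- **One scheduled post-baseline sample:** make the main analysis multiple imputation of the missing Week 24 value followed by the ANCOVA already specified.

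In either case keep the runs with and without post-rescue data, and keep LOCF-ANCOVA as a sensitivity analysis.

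The cost is a change of SAP wording, one more table and a small amount of programming; the SMPG program can be reused for the MMRM. Both replacements assume that data are missing at random, which cannot be verified. The retained LOCF analysis gives a comparison under a different assumption.

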### **5.13.2. Percentage of Patients Achieving a Target HbA1c $\leq 6.5\%$**

For percentages of patients achieving target HbA1c of  $\leq 6.5\%$  at 24 weeks, longitudinal logistic regression with repeated measurements (generalized linear mixed models, Liu and Zhan 2011) will be used. The model will include independent variables for treatment, country, SGLT2 inhibitor dose (“low” versus “high”), metformin use (“yes” versus “no”), visit, baseline HbA1c - by-visit interaction, and treatment-by-visit interaction as fixed effects, and baseline HbA1c as a covariate. These analyses will be performed with post-rescue data excluded (considered missing), and separately with all post-rescue data included. In addition, an analysis of percentage of patients on HbA1c targets will be performed where patients who have been rescued or have no post-baseline data will be considered (imputed) as not having achieved the target.

### **5.13.3. Analysis of 6-point SMPG profile**

The 6-point self-monitored plasma glucose (SMPG) profiles consist of pre-meal and 2-hour postprandial SMPG measurements for the morning, midday, and evening meals.

The following variables for 6-point SMPG profile will be analyzed using MMRM:

1. Pre morning meal plasma glucose (PG) (mg/dL)
2. 2-hour postprandial measurement for morning meal PG (mg/dL)
3. Pre midday meal PG (mg/dL)
4. 2-hour postprandial measurement for midday meal PG (mg/dL)

5. Pre evening meal PG (mg/dL)
6. 2-hour postprandial measurement for evening meals PG (mg/dL)
7. Mean of all pre-meals PG (mg/dL)
8. Mean of all postprandial PG (mg/dL)
9. Mean of all meals 2-hr excursion (mg/dL)
10. Mean of all 6-point PG (mg/dL)

For mean of all pre-meals PG (Report 7), the pre-meal daily mean is calculated as the average PG values collected for before morning, midday and evening meals on a particular day. The change from baseline is calculated as the mean of all pre-meals PG at Week 12 and Week 24 minus the mean of all pre-meals PG at baseline.

For mean of all postprandial PG (Report 8), the post-meal daily mean is calculated as the average of 2-hour postprandial PG values of morning, midday and evening meals on a particular day. The change from baseline is calculated as the mean of all postprandial PG at Week 12 and Week 24 minus the mean of all postprandial PG at baseline.

For mean of all meals 2-hour excursion at each visit (Report 9), the daily mean for all meals is calculated as the average of glucose excursion for morning, midday and evening meals on a particular day. The change from baseline is calculated as the mean of all meals 2-hour excursion at Week 12 and Week 24 minus the mean of all meals 2-hour excursion at baseline.

For mean of all 6-point PG (Report 10), the daily mean is calculated as the average of 6 PG values collected on a particular day. The change from baseline is calculated as the mean of all 6-point PG at Week 12 and Week 24 minus the mean of all 6-point PG at baseline.

Change from baseline of 6-point SMPG values will be summarized using the ITT population, and analyzed using MMRM with treatment, country, SGLT2 inhibitor dose (“low” versus “high”), metformin use (“yes” versus “no”), visit, baseline HbA1c strata ( $\leq 8.0\%$  and  $> 8.0\%$ ) and treatment-by-visit interaction as fixed effects, baseline 6-point SMPG as a covariate and patient as a random effect. An unstructured covariance structure will be used to model the within-patient variability and implicitly adjusts for missing data. If this analysis fails to converge, then other covariance structures will be tested in the order mentioned in Section 5.2.

#### **5.14. Pharmacokinetic/Pharmacodynamic Analyses**

Not Applicable for this study.

#### **5.15. Safety Analyses**

The safety analysis will include the assessment of adverse events (AEs), serious adverse events (SAEs), special safety topics, laboratory analytes, vital signs, and electrocardiograms (ECGs). Unless otherwise specified, the ITT population will be used for analyses of the safety measurements.

### 5.15.1. Adverse Events

An adverse event (AE) is any untoward medical event associated with the use of a drug in humans, whether or not it is considered related to a drug. Adverse events will be coded from the actual term described by the investigator using the Medical Dictionary for Regulatory Activities (MedDRA). Unless otherwise specified, AEs will be reported using the MedDRA system organ class (SOC) and preferred term (PT). Selected AEs may be reported using MedDRA high-level terms (HLT).

All AEs will be listed by investigator by patient using MedDRA PT.

Treatment-emergent adverse events (TEAEs) are defined as an event that first occurs or worsens (increases in severity) after the first dose on Visit 5.

Summary statistics will be provided for TEAEs, SAEs, and study discontinuation due to AEs or death during the treatment period. Counts and proportions of patients experiencing AEs will be reported for each treatment group, and chi-square tests will be used to compare the treatment groups.

Since gastrointestinal (GI) AEs, like nausea and vomiting, are among the most common events reported in patients treated with dulaglutide, summaries and analyses for onset, duration, and severity of nausea and vomiting will be provided.

Listings of patients experiencing allergic and hypersensitivity reactions, as well as those discontinuing the study due to AE will be produced.

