## 5. A Priori Statistical Methods

### 5.1. Determination of Sample Size

With 120 completers per arm, the study will have 90% power for demonstrating superiority of either dulaglutide 1.5 mg or 0.75 mg versus placebo in change from baseline in mean hemoglobin A1c (HbA1c) at 24 weeks, assuming a standard deviation (SD) of 1.2%, a difference between dulaglutide and placebo of 0.55%, and a 2-sided significance level of 0.025. Assuming that the dropout rate is 15% for the entire study period, the study will need to enroll at least approximately 142 patients in each arm for a total of 426 patients enrolled. Assuming a screen fail rate of 40%, a total of approximately 710 patients will be screened to meet these enrollment number requirements.

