**Table GBGE.5.1. Analysis Populations**

Population	Definition
All Entered	All patients who signed informed consent forms (ICF)
All Randomized	All patients who were randomized to a treatment arm
Non-randomized	All patients who entered, but not randomized, to a treatment arm
Intent-to-treat (ITT)	All randomized patients who have taken at least one dose of the study medication
Per-protocol (PP)	All patients in ITT and who also meet the following criteria: 
 
• Have no important protocol deviations (Section 5.7)
 
• Completed the treatment phase (24 week [Visit 11]) for primary end point (ie, did not discontinue from the study early)
 
• Are at least 75% compliant with study drug for at least 75% of the visits
 

Completer Population	The completers population will be defined as those who: 
 
• Completed the treatment period (ie, did not discontinue early from the study)
 

The complete list of protocol deviations leading to exclusion from the PP population is provided in Section 5.7.

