## 5.5. Patient Disposition

A listing of patient discontinuation will be presented for all randomized patients. Frequency counts and percentages of all patients entered, randomized/enrolled, completing and discontinuing from the study and study treatment will be presented for all treatment groups. A summary of discontinuations will also be presented by visit. The overall percent discontinued comparisons among the treatments will be performed using a Chi-square test or Fisher's exact test.

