## 5.10. Treatment Exposure

Treatment exposure is defined as the time from when the patient is randomized at Visit 5 and receives study drug until the patient either discontinues from treatment or completes the treatment period as planned.

The duration of treatment exposure will be listed and summarized by treatment group for ITT, PP, and completer populations. Duration of exposure will be categorized into the following groups:  $\leq 14$  days,  $>14$  to  $\leq 28$  days,  $>28$  to  $\leq 56$  days,  $>56$  to  $\leq 84$  days,  $>84$  to  $\leq 126$  days,  $>126$  to  $\leq 168$  days and  $>168$  days. These categories will be summarized as frequency by treatment group. Summary statistics will include mean per patient exposure in days, SD, median, min, and max. The duration of treatment exposure will be analyzed using one-way ANOVA with treatment as fixed effect.

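### AE-related discontinuation is summarised only as leaving the study; stopping study drug for an AE has no planned count, so the Table GBGE.4.1 endpoint could be undercounted

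*SAP*

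**What the plan says.** Table GBGE.4.1 lists "Early discontinuations due to AEs" among the secondary safety endpoints to be compared between each dulaglutide dose and placebo at 24 weeks. It does not say whether the study or the study drug is discontinued.

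Section 5.15.1 is where the endpoint becomes an analysis: "Summary statistics will be provided for TEAEs, SAEs, and study discontinuation due to AEs or death during the treatment period". The matching listing covers patients with allergic and hypersensitivity reactions, "as well as those discontinuing the study due to AE will be produced". Both are limited to leaving the study.

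Elsewhere the SAP separates the two events. Section 5.5 plans counts and percentages of patients "completing and discontinuing from the study and study treatment will be presented for all treatment groups". Section 5.10 measures exposure "until the patient either discontinues from treatment or completes the treatment period as planned".

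Table GBGE.5.1 points the other way. It defines a completer as someone who "Completed the treatment period (ie, did not discontinue early from the study"), which reads as if finishing treatment and not leaving the study were the same thing.

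**The concern.** Stopping the drug because of an AE bears directly on tolerability, and it need not coincide with leaving the study. Section 5.15.1 counts only the second event. Take a patient who stops injections at week 3 because of nausea but attends through Visit 11. The nausea is recorded as a treatment-emergent AE and the stop enters the Section 5.5 totals, but neither the Section 5.15.1 summary nor its listing shows that an AE ended treatment.

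Section 5.15.1 itself says that nausea and vomiting are among the commonest events on dulaglutide, so AE-related stops may well be more frequent on the active arms. Losing some of them would lower the reported rates there and could make the arms look more alike on this endpoint than they are.

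**Working it through.** The point rests mainly on wording; the SAP states no AE-discontinuation rate to reproduce.

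**Step 1. The sections side by side.**

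| Place in SAP | Event | Tied to an AE? |
|---|---|---|
| Table GBGE.4.1 | early discontinuation, from what not stated | yes |
| 5.15.1 summary | leaving the study | yes (or death) |
| 5.15.1 listing | leaving the study | yes |
| 5.5 disposition | leaving the study, and stopping study treatment | no reason stated |
| 5.10 exposure | stopping treatment | no reason stated |

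The missing combination is stopping study treatment because of an AE. The AE tables give the event and Section 5.5 gives the stop, but no planned output links them.

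**Step 2. What would be counted.** Let p be the true proportion of an arm that stops drug for an AE and s the share of those who stay in the study. Section 5.15.1 then reports p × (1 − s). Neither p nor s is in the SAP; both are assumed. The arm size is from Section 5.1: 120 / (1 − 0.15) = 141.2, rounded up to 142, and 3 × 142 = 426, which agrees with "the study will need to enroll at least approximately 142 patients in each arm for a total of 426 patients enrolled". The 15% dropout there is not split by reason or by drug versus study, so it fixes neither p nor s.

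Patients counted out of 142, with the reported rate:

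| p (true stops) | s = 0 | s = 10% | s = 25% | s = 50% |
|---|---|---|---|---|
| 3% (4.3) | 4.3 (3.0%) | 3.8 (2.7%) | 3.2 (2.25%) | 2.1 (1.5%) |
| 5% (7.1) | 7.1 (5.0%) | 6.4 (4.5%) | 5.3 (3.75%) | 3.6 (2.5%) |
| 8% (11.4) | 11.4 (8.0%) | 10.2 (7.2%) | 8.5 (6.0%) | 5.7 (4.0%) |

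At s = 0 nothing is lost.

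**Step 3. The comparison between arms.** Assume 10 AE-related drug stops on one dulaglutide arm (10/142 = 7.0%) and 3 on placebo (3/142 = 2.1%), with the same s in both.

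| s | Dulaglutide | Placebo | Difference (points) |
|---|---|---|---|
| 0 | 7.0% | 2.1% | 4.9 |
| 25% | 5.3% | 1.6% | 3.7 |
| 75% | 1.8% | 0.5% | 1.2 |

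The absolute difference shrinks by the factor (1 − s). The ratio stays at 10/3, about 3.3.

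**Step 4. Unequal retention.** The difference is understated only if more AE-related stops go uncounted on dulaglutide than on placebo. With the same 10 and 3 stops, if 4 dulaglutide patients and 1 placebo patient stay in, the reported difference is (6 − 2)/142 = 2.8 points. If none and 1 stay in, it is (10 − 2)/142 = 5.6 points, which is above the true 4.9. The rates themselves can only be too low.

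**The case against.** The strongest objection is that the SAP never shows that a patient can stop drug for an AE and remain in the study. A reader might infer this from the treatment-regimen estimand added in Version 2, which uses values obtained on additional or alternative glucose-lowering agents. The documents do not support that inference: Sections 3 and 5.2 define the estimand by its use of post-rescue data and say nothing about following patients who stop injections for an AE. The completer definition in Table GBGE.5.1 leans towards treating the two events as one. Whether such patients stay is a protocol matter, and the protocol was not available for this check. If they must leave, Section 5.15.1 catches every case. This stands, and it makes the harm conditional.

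A reader might also conclude that these patients vanish from the report or that intolerance is understated. Neither follows. The patients are in the Section 5.5 treatment-discontinuation counts, the exposure summary, the AE tables and, where relevant, the nausea and vomiting analyses; only the link between the stop and the AE is missing. Section 5.5 is silent on reasons, so its tables may turn out to show them, but nothing commits the sponsor to that.

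It is also fair to say that reading the endpoint as study discontinuation is permissible, since Table GBGE.4.1 does not specify. Section 5.15.1 therefore does not contradict the table. What remains is that the SAP distinguishes the two events and then plans an AE-attributed analysis of only one, without saying that this is the intended endpoint.

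**Conclusion.** The point holds in a limited, conditional form. As written, Section 5.15.1 can undercount a named secondary safety endpoint, because AE-related stopping of study drug has no planned summary, comparison or listing. Whether it does so depends on whether any patients stop drug for an AE and stay in the study, which the SAP does not settle. The size is unknown: the tables above are illustrations on assumed rates, and they include the case of no loss. Where there is a loss, the rates are too low. The absolute difference between arms is too small if retention is equal and dulaglutide has more AE-related stops, or more generally if more stops go uncounted on dulaglutide. With equal retention the ratio of rates is unaffected.

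The endpoint lies outside the graphical testing scheme, so no primary or key secondary conclusion depends on it. The change is still worth making, because it removes an ambiguity in the tolerability comparison at almost no cost.

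**What to change.** In Section 5.15.1, summarise, compare by arm and list discontinuation of study drug due to an AE (including death), beside study discontinuation due to an AE. State which of the two is the Table GBGE.4.1 endpoint. Widen the listing to patients who discontinue either study drug or the study because of an AE.

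The cost is a sentence or two of SAP text, one table row and a wider listing; Section 5.5 already plans counts of study-treatment discontinuation. The reported AE-discontinuation rate may look slightly less favourable. If every patient who stops drug also leaves the study, the new row adds no AE-related stops beyond those already counted, and nothing else changes.
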